5.5 APPROPRIATENESS OF MEASUREMENTS

Standard methods will be used as measures conducted for both primary and secondary endpoints. Measures conducted for exploratory further endpoints might be new

methodologies that have already been used in clinical trials in LN but not yet validated for this rare disease. This includes measurements of patient reported outcomes e.g. Lupus Pro and Facit-F.

6. INVESTIGATIONAL PLAN

6.1 VISIT SCHEDULE

All patients are to adhere to the visit schedule as specified in the Flow Charts. If any visit needs to be rescheduled outside of the protocol allowed window, approval must be obtained from the CTM/CTL and subsequent visits should follow the original visit schedule.

Additional unscheduled visits might be arranged at the discretion of the investigator (e.g. in case of relapses). For unscheduled visit, it is sufficient to record only the clinically relevant laboratory parameters and safety findings in the patients' medical records and on the adverse event eCRF. During or at the end of each visit, site must register the respective visit in IRT for each patient.

For a detailed overview of the trial procedures and the acceptable time windows for each visit, please refer to the [Flow Charts](#).

In exceptional cases, if standard visits at the trial sites are impossible because of COVID-19 related safety risks or local restrictions, the following trial procedures may be performed remotely, e.g. via telephone and/or internet based means of communication, as locally allowed:

- Collection of information of existing or new adverse events
- Confirming current or new concomitant medication or dose changes
- SLE-disease state
- Compliance check, including study drug injections and the use of the diary
- Outcome of home pregnancy test, if applicable

In addition the following alternatives to study procedures may be used

- Lab procedures: in case critical study visits such as week 12, 26, 42 and/or 52 cannot be done at the clinical site, the patient will be asked to have at least certain parameters (hematology, chemistry, urine tests, C3/C4 and Anti-dsDNA) tested in a local lab if possible. The results of the lab tests must be transferred to the investigator who ensures medical review and proper documentation in the eCRF.
- If a 24 hr urine sample will be required per protocol, the respective containers should be shipped to the patient and UP/UC-values measured in a local lab.
- If patients' questionnaires will be required per protocol, these should be sent to the patient's home and completed by the patient. It is considered to be an appropriate measure as all patients have previously completed such questionnaires at the site and are familiar with their use.
- The investigator may ask the patient to measure the body temperature and weight at home and verbally report to the investigator. If the patient is also not allowed to pick up re-supply of investigational product at the site, a direct to patient's home shipment may be arranged by using a BI-qualified courier service.

All of the above mentioned workarounds shall only be performed after prior approval by CTL or TMM and with the consent by the patient (preferred in writing, but verbal consent possible) and if local regulations do allow such exceptional measures.

All remote visits need to be discussed with and approved by the sponsor's trial team. Local regulatory and legal requirements of the participating country still apply.

In case of strict movement restrictions in a certain region and no workarounds are possible, the following applies

- If a patient has to interrupt treatment with investigational product for more than 6 weeks the patient shall be discontinued from the trial.
- If no safety lab can be taken for more than 12 weeks, the patient shall be discontinued from the trial.

All COVID-19 related deviations from the original schedule of visits and procedures will be documented and the implications considered for the analysis of the trial data.

6.2 DETAILS OF TRIAL PROCEDURES AT SELECTED VISITS

Refer to the study [Flow Charts](#) for a detailed description of trial procedures during the trial period. Only additional and critical information are outlined below.

6.2.1 Baseline (Group 1)

Written informed consent must be obtained prior to any study related procedures or assessments are being performed.

For roll-over patients (Group 1), the preliminary decision on renal response for participation in this trial will be based on laboratory results from visit 15 of the 1293.10 trial.

In case visit 15 of the 1293.10 trial cannot be used to come to a clear roll over decision, V16 /EOT-results can be used. It is preferred to use the results from the 24 hr urine collection, however UP/UC-results from spot urine are also acceptable.

The baseline visit must take place on the same day or at a maximum within 3 days from EOT visit of the 1293.10 trial. All assessments performed at the 1293.10 EOT visit will be used as baseline assessments for this trial and should not be repeated.

In case the baseline visit could not be performed on the same day or within 7 days from the 1293.10 EOT visit, approval must be obtained from the CTM/CTL prior to proceeding.

In case the baseline visit will be later than 7 days after EOT of 1293.10, selected lab values shall be repeated (biochemistry, hematology, Anti-dsDNA complement C3/C4 and serum creatinine and UP/UC).

In case the treatment interruption between the trials is longer than the above mentioned timeframe, in exceptional cases patients can roll over for ethical reasons. Please refer to [section 4.1.4](#).

For a detailed description of the trial procedures at the baseline (Group 1) visit, please refer to [Flow Charts](#).

Baseline Conditions and Medical History

As a precaution, risk factors for thromboembolic disease (including medical history of DVT/TE) should be specifically checked. If clinically relevant, the case should be discussed with the CTL prior to enrollment.

History of antiphospholipid syndrome should be recorded and patients should be excluded from the study.

6.2.2 Treatment period

Patients from Group 1 will not be randomised as they will continue receiving the same treatment allocation as previously assigned in 1293.10. Patients will receive the first dose of study medication at Visit 1, after all eligibility criteria have been confirmed, to ensure no interruption to their current treatment.

Investigators will not be given access to the treatment information of roll over patients until the trial is completed.

The 24hr urine collections will be performed for endpoint assessments at the visits indicated in the Flow Charts. Patients will be given instructions and materials to allow the collection of 2 x 24hr urine samples during the week before the scheduled visit. At all other visits, proteinuria will be assessed by spot urine.

In general, if several procedures including venepuncture are scheduled at the same time point, venepuncture should be performed last due to its inconvenience and possible influence on subject's physiologic parameters.

At any visit, should a decision be made to discontinue the patient from study medication, please complete EOT visit instead.

For a detailed description of trial procedures during the treatment period, refer to [Flow Charts](#).

Any treatment interruption of more than 2 consecutive missed injections shall be communicated to the CTL.

6.2.3 Follow up period and trial completion

6.2.3.1 End of Treatment (EOT) Visit

The EOT visit will be performed within 7 days after the last administration of trial medication in all patients who either complete the 52-week treatment period or prematurely discontinue the study medication for any reason.

For a detailed description of the trial procedures at EOT, refer to [Flow Charts](#).

6.2.3.2 Follow-Up (FUp) and End of Study (EOS) Visits

After the EOT visit, patients who have completed the 52-week treatment period will return for a safety FUp visit 4 weeks later, followed by the EOS visit 12 weeks after EOT. In case a patient has to discontinue the trial medication prior to having completed the 52-week treatment period, the patient will be invited to attend a subset of visits as per [section 6.2.3.3](#) below.

The investigator will continue to record and follow-up on all AEs until the residual effect period (REP). Refer to [section 5.2.5.2](#) for AE collection procedures after the REP. At EOS visit, the investigator needs to confirm whether the AEs are sufficiently followed up and provide documentation in the patient's medical records and on the eCRF.

For a detailed description of the trial procedures at FUp and EOS visits, refer to [Flow Charts](#).

6.2.3.3 Additional follow-up for prematurely discontinued patients

For prematurely discontinued patients, it is important that their renal function parameters and safety assessments are performed and recorded until the end of the 52-week period. Therefore, all early discontinued patients will be invited to attend a subset of FUp visits at the following time points: Week 12, Week 26, Week 42 and Week 52.

At these FUp visits, the following assessments will be performed: physical examination, AE and CT collection, serum creatinine and spot urine test to assess renal function. Other safety laboratory tests, PK, ADA, soluble protein biomarkers, anti-ds-DNA and complement levels will be collected at these visits.

If the next FUp visit is planned more than 12 weeks after EOT, all optional tests shall be performed at least once in the FUp period: i.e. if the patient EOT is at week 26 and the next visit will be only at week 42: optional tests must be done at week 42, even if the time between week 26 & 42 is >12 weeks.

During the additional follow-up period, after the patients have discontinued the trial medication and have been followed-up for 4 weeks, the patients will be allowed to participate in another investigational study whilst continue to attend these additional study visits as described above.

In case the patient discontinued more than 12 weeks before week 52, no additional follow up visits would be required after week 52. In case the patient discontinued less than 12 weeks before week 52, the last follow-up visit will be 12 weeks +/- 5 days after discontinuation.

In case the patient was unable to attend these additional study visits, vital status information will be collected at - Week 52 or 64 depending on discontinuation date (see above).

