3.2 DISCUSSION OF TRIAL DESIGN, INCLUDING THE CHOICE OF CONTROL GROUP

The design of this trial together with the 1293.10 (dose-finding, efficacy and safety of BI 655064 in patients with active LN) is intended to facilitate the selection of appropriate dose regimens for further confirmation in the Phase III trials.

The treatment duration of 52 weeks was selected based on feedback from external experts and recommendation in the currently available EMA guideline for at least one year maintenance treatment following induction therapy for LN ([R15-3716](#)).

Group 1 are patients that have achieved a renal response or proteinuria ≤ 1.0 g/d (or UP/UC ≤ 1) at the end of 1293.10; it is therefore justifiable for these patients to continue receiving the same treatment arm as previously assigned in 1293.10 during the maintenance phase. This is to ensure both patients and investigators remain blinded in order to allow comparisons of efficacy and safety of different doses in a population that appears to be able to safely receive the same dose as in the 1293.10 induction study. The patients will continue to receive one injection per week at Visit 1 of either BI 655064 (120mg/180mg/) or Placebo for up to 52 weeks (12 months). Patients on 240mg receive one injection of 120mg every week.

After topline data from trial 1293.10 became available, an independent DMC reviewed these topline data and unblinded safety and efficacy data of Group 1 patients in trial 1293-0013. The DMC recommended to continue trial 1293-0013 as planned.

The Boehringer Ingelheim Benefit Risk Committee (BRC) assessed the benefit-risk of BI 655064 for patients in Group 1 of trial 1293 13 (responders from trial 1293.10). The BRC took into consideration the recommendation to continue the trial given by the DMC and concluded that the benefit-risk for patients in Group 1 of trial 12930013 is unchanged for responders but decided that investigators should be informed about topline data and should receive treatment information for those patients remaining in Group 1 of trials 1293-0013. The investigator and the patient should thoroughly discuss treatment options and the patient's continuing participation in 1293-0013. Following this decision, a total of 29 patients (20 on treatment, 9 in follow-up) were unblinded.

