4.1.5 Blinding and procedures for unblinding

4.1.5.1 Blinding

In this double-blind trial, all patients, investigators and sponsor staff (except those BI members independent of the trial team that will perform the primary analysis) will remain blinded with regard to the randomised treatment assignments.

After the final analysis of the preceding trial 1293.10 it was revealed that the primary endpoint was not reached. An independent DMC reviewed the topline results of 1293.10 and unblinded efficacy and safety results of the ongoing Group 1 in trial 1293-0013 and recommended to continue trial 1293.0013. Taking this recommendation into consideration, a Benefit Risk Committee concluded that the benefit-risk for patients in Group 1 of trial 1293-0013 is unchanged but decided that treatment of patients remaining in the trial should be unblinded.

The unblinding step was taken on 20 Oct 2020 and communicated to the applicable investigators. All other patients who had already completed or early discontinued the trial at that timepoint and were no longer in follow up remain blinded.

For the remaining patients who were not unblinded, a limited number of sponsor personnel will have the potential to be unblinded; however, sponsor personnel involved in the conduct of 1293-0013 (e.g. trial monitor and local monitors) will remain blinded until completion of 1293-0013. These investigators and patients will also remain blinded until completion of the trial.

For Group 1 IRT will be used in 1293.10 for the assignment of patients to treatment groups and the randomisation sequence generated using validated software and verified by an independent BI statistician who is not involved in the planning or performance of the trial. The randomisation code will be kept confidential by Clinical Trial Support up to DBL. For Group 1.

The randomisation codes will be provided to bioanalytics prior to last patient out to allow for the exclusion from the analyses of pharmacokinetic (PK) samples taken from placebo patients. Bioanalytics will not disclose the randomisation code or the results of their measurements until the trial is officially unblinded.

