4.2.3 Restrictions

4.2.3.1 Restrictions regarding concomitant treatment

Concomitant medications (or therapy) to provide adequate care may be given as clinically necessary. If a restricted concomitant therapy is required, treatment with trial medication should be permanently discontinued.

Table 4.2.3.1:1 Permitted and restricted medications

Therapy	Treatment Period	Follow up Period
MMF	Permitted if dose $\leq 1-2 \text{ g/d}^*$	Permitted
Azathioprine	Permitted if dose $\leq 2 \text{ mg/kg}$	Permitted
Abatacept or Cyclophosphamide	Not permitted	Not Permitted
Cyclosporine / Tacrolimus / Mizoribine	Not permitted	Permitted if required as per investigator's decision
Belimumab or other "anti- BLYS" or another investigational drug	Not permitted	Not permitted
Biologic B-cell depleting therapy (e.g. anti-CD20)	Not permitted	Not permitted
IV glucocorticoids	Not Permitted	Permitted

¹: for group 1 patients, the doses for MMF and AZA are given in 1293.10 are acceptable to be continued throughout 1293-0013 as long as the patient otherwise qualifies for roll over.

*exception see [section 4.2.1](#).

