5.2.5.2 Adverse event collection and reporting

AE Collection

The investigator shall maintain and keep detailed records of all AEs in the patient files. The following must be collected and documented on the appropriate eCRF(s) by the investigator:

- From signing the informed consent onwards until the individual patient's end of study:
 - All AEs (serious and non-serious) and all AESIs.
- Patients who discontinue trial medication prematurely and agree to be contacted further, should be followed up as described in [section 3.3.4.1](#). From then on until the individual patient's end of the trial:
 - The investigator must report all deaths/fatal AEs regardless of relationship; related SAEs and related AESIs that the investigator becomes aware of.
- After the individual patient's end of study:
 - The investigator does not need to actively monitor the patient for AEs but should report related SAEs and related AESIs of which the investigator may become aware of by any means of communication, e.g. phone call. Those AEs should, however, not be reported in the eCRF.

[figure not shown]

Figure 5.2.5.2: 1 AE Collection

The REP is defined as 50 days after the last trial drug administration. All AEs that occur during the treatment phase and throughout the REP will be considered as on treatment (see [section 7.3.4](#)). Events that occur after the REP will be considered as post treatment events.

AE reporting to sponsor and timelines

The investigator must report SAEs, AESIs, and non-serious AEs which are relevant for the reported SAE or AESI, on the BI SAE form immediately (within 24 hours) to the sponsor's unique entry point (country specific reporting process will be provided in the ISF). The same timeline applies if follow-up information becomes available. In specific occasions the investigator could inform the sponsor upfront via telephone. This does not replace the requirement to complete and send the BI SAE form.

With receipt of any further information to these events, a follow-up SAE form has to be provided. For follow-up information the same rules and timeline apply as for initial information.

Information required

For each AE, the investigator should provide the information requested on the appropriate eCRF pages and the BI SAE form, if applicable. The investigator should determine the causal relationship to the trial medication and any possible interactions between the trial medication and an Auxiliary Medicinal Product (AMP).

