7.3.4 Safety analyses

Adverse events will be coded using the Medical Dictionary for Drug Regulatory Activities (MedDRA). Standard BI summary tables and listings will be produced. All adverse events with an onset between start of treatment and end of the residual effect period (REP), a period of 50 days after the last dose of trial medication, will be assigned to the on-treatment period for evaluation. Analysis will be performed based on randomised treatment.

All treated patients will be included in the safety analysis. In general, safety analyses will be descriptive in nature and based on BI standards. No hypothesis testing is planned. Statistical analysis and reporting of adverse events will concentrate on treatment-emergent adverse events, i.e. all adverse events occurring between start of treatment and end of the REP. Adverse events that start before first drug intake and deteriorate under treatment will also be considered as 'treatment-emergent'.

Frequency, severity and causal relationship of adverse events will be tabulated by system organ class and preferred term after coding according to the current version of the MedDRA at the database lock.

AESIs will be summarized separately using a standard BI summary table. Note that there is one SAE definition specified in [Section 5.2.5.1](#) for Japan only. Laboratory data will be analysed both quantitatively as well as qualitatively. The latter will be done via comparison of laboratory data to their reference ranges. Values outside the reference range as well as values defined as clinically relevant will be summarised. Treatment groups will be compared descriptively with regard to distribution parameters as well as with regard to frequency and percentage of patients with abnormal values or clinically relevant abnormal values.

Vital signs, physical examinations, or other safety-relevant data observed at screening, baseline, during the course of the trial and at the end-of-trial evaluation will be assessed with regard to possible changes compared to findings before start of treatment.

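### Protocol 6.2.3.3 lets early stoppers join another investigational study before the 50-day residual effect period ends, Table 4.2.3.1:1 says otherwise, and the visible SAP does not flag the overlap

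*Protocol*

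**What the plan says.** Four parts of the plan bear on this.

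- **The permission.** Protocol 6.2.3.3 deals with patients who stop trial medication early. Once they "have been followed-up for 4 weeks, the patients will be allowed to participate in another investigational study whilst continue to attend" the additional visits planned up to week 52.
- **The restriction.** Protocol Table 4.2.3.1:1 has a row for belimumab, similar agents "or another investigational drug". It is marked as not permitted in both the treatment and the follow-up column. The table does not cite 6.2.3.3, and 6.2.3.3 does not cite the table.
- **The attribution window.** Protocol 5.2.5.2 states: "The REP is defined as 50 days after the last trial drug administration". Protocol 7.3.4 and SAP 6.1 and 7.8.1 count adverse events up to that point as on treatment, under the randomised arm. SAP 6.1 and 7.8.2 apply the same window to laboratory samples. Follow-up starts on day 51.
- **Handling of a second product.** SAP deviation D1 names another investigational drug only for the treatment period, and SAP 6.1 ends that study period at the last dose. SAP 7.2 lists concomitant medication by patient. Nothing in the visible SAP links a second investigational product to the attribution of adverse events or laboratory values.

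**The concern.** The 4-week wait is shorter than the period in which the trial itself assumes a residual effect of its drug. A patient who stops early, waits 4 weeks and starts a second investigational product would still be inside the on-treatment window. A reportable event caused by that product would appear in the tables under BI 655064 or placebo.

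The conflict with Table 4.2.3.1:1 adds to this, because a site cannot tell from the protocol which rule applies. At stake are the clarity of small-arm safety tables and a possible overlap of a second drug with residual BI 655064. Safety is a main objective, and Protocol 5.2.5.1 describes the drug as immunosuppressive, with severe and opportunistic infections as events of special interest. Such events would be hard to attribute if the second product were also immunosuppressive, which is plausible but not stated.

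**Working it through.** The documents state no overlap figure, so there is none to reproduce.

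**Inputs from the documents**
- Wait: 4 weeks = 28 days (Protocol 6.2.3.3). The flow chart agrees that EOT+4 is 393 − 365 = 28 days.
- REP: 50 days after the last dose (Protocol 5.2.5.2).
- EOT visit: 0 to 7 days after the last dose (Protocol 6.2.3.1).
- Expected patients: about 60 (Protocol 7.7).
- Follow-up visits of early stoppers: weeks 12, 26, 42 and 52 (Protocol 6.2.3.3), which are days 85, 183, 295 and 365 in the flow chart.

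**Overlap = REP − (lag to start of the 4 weeks + 28)**
- 4 weeks from the last dose: 50 − (0 + 28) = 22 days.
- 4 weeks from an EOT visit 7 days later: 50 − (7 + 28) = 15 days.

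These are upper bounds. The overlap is shorter if dosing in the other study starts later, and zero if that study gives no drug or if Table 4.2.3.1:1 governs. Applying the flow chart's ±5-day visit window would give 10 to 27 days, but 6.2.3.3 states no window for the wait.

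**Patients affected (rates are assumptions; the documents give none)**
Assume 10% to 30% stop early and 5% to 20% of those start another investigational drug before day 51.
- Low: 60 × 0.10 × 0.05 = 0.3 patients.
- High: 60 × 0.30 × 0.20 = 3.6 patients.

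**Scheduled laboratory samples in the overlap**
Assume stops are spread evenly over 364 days. A visit falls in the overlap if it comes 29 to 50 days (or 36 to 50 days) after the last dose.
- 22 × 4 visits = 88 stop days; 88/364 = 24.2%.
- 15 × 4 visits = 60 stop days; 60/364 = 16.5%.
- Patients with such a sample: 0.3 × 0.165 = 0.05 to 3.6 × 0.242 = 0.87, so fewer than one.

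**Worst-case shift in an adverse event rate**
Assume 10 to 20 patients per arm (SAP 7.4.1 says only that the arms are not balanced). One patient then moves a rate by 1/20 = 5 points to 1/10 = 10 points.

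SAP 7.8.1 counts patients, not events, and SAP 6.1 starts the treatment period at the first dose in 1293.10. With about 364 days there and up to 364 here, an early stopper's window is about 364 + 50 = 414 to 728 + 50 = 778 days. The overlap is 15/778 = 1.9% to 22/414 = 5.3% of it. A patient who already had that event type adds nothing.

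**Renal response**
Under SAP 6.6.1 an early stopper is a non-responder, is evaluated at discontinuation, or is non-evaluable. Data collected after a second product starts do not enter CRR or PRR under these rules.

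**The case against.** The strongest reply is that the hazard exists on one reading only. If the follow-up column of Table 4.2.3.1:1 governs, no second product is taken and the overlap is zero. This stands as a condition on the point. It does not remove the need to reconcile two texts that give sites different instructions. Section 6.2.3.3 is probably the intended exception, but the protocol does not say so.

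Second, few events may be captured. After premature discontinuation, Protocol 5.2.5.2 says: "The investigator must report all deaths/fatal AEs regardless of relationship; related SAEs and related AESIs that the investigator becomes aware of". Relatedness there is judged against the trial medication, so a non-fatal event blamed on another product might never be reported. Protocol 6.2.3.2, however, has all adverse events recorded until the REP, and 6.2.3.3 includes adverse event collection at the additional visits. The breadth is unsettled; deaths count on every reading.

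Third, much can be traced by hand. Concomitant therapy is collected at these visits and listed by patient, and Protocol 5.2.5.1 tells investigators to weigh concomitant medication in judging causality. SAP 6.7 gives the later visits of early stoppers their own follow-up labels, so by-visit laboratory displays are largely separated. The 50-day rule still brings such samples into the report's Section 15 tables and abnormality summaries. The sponsor guideline cited in SAP 7.8.1 may contain a rule, but it cannot be seen here.

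A reader might infer that the safety comparison or the primary endpoint is compromised. The documents do not support that. Safety analysis is descriptive, the 5 to 10 point shift needs a new event type in an affected patient, and CRR and PRR of early stoppers under SAP 6.6.1 are untouched.

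**Conclusion.** The gap is real but small. The protocol gives two unreconciled rules on another investigational drug in follow-up. If 6.2.3.3 governs, up to 22 days (or 15) of possible exposure to a second product would count as on-treatment for the randomised arm, unflagged in the visible SAP.

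The day counts rest on the documents. The 0.3 to 3.6 patients, the laboratory figure and the 5 to 10 point shift rest on assumed rates and arm sizes. The shift is a worst case, not an expected effect. This is a low-priority, cheap improvement and no threat to the main result.

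**What to change.** - **Protocol 6.2.3.3:** allow dosing with another investigational drug only more than 50 days after the last dose of trial medication.
- **Protocol Table 4.2.3.1:1:** cross-reference that exception in the follow-up column.
- **SAP 6.1, 7.8.1 and 7.8.2:** for any patient who starts another investigational drug before day 51, flag adverse events and laboratory values from that start date. Keep the 50-day window in the main tables so that delayed BI 655064 effects are not lost. Show the affected tables without the flagged data only if such patients exist.

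The cost is one sentence, one cross-reference and one flag built on concomitant therapy data already collected. The protocol change comes late: "The unblinding step was taken on 20 Oct 2020", when "a total of 29 patients (20 on treatment, 9 in follow-up) were unblinded". At most 20 patients, or 20/60 = 33% of the expected number, could still stop early after that date. The SAP flag also covers those who stopped before.

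The downside is that early stoppers, including some with a flare, would wait about 2 to 3 weeks longer (15 to 22 days) for another investigational drug, and some might withdraw consent instead. If that is not acceptable, the table cross-reference and the SAP flag alone suffice.
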